recruitment of mental health experts, participant incentives, recording of interviews, and transcription and analysis of these interviews. Members of the ESTEEM lab's clinical team will conduct the interviews. Phase 3 will involve pilot testing the adapted cognitive-behavioral treatment through a randomized controlled trial with 60 SMW who report experiencing depression, anxiety, and alcohol abuse. The SMW will be randomized to either therapy or waitlist. Individuals assigned to therapy will receive 10 weekly individually-delivered sessions, directly after baseline assessment, that address minority stress mechanisms underlying SMW's depression, anxiety, and alcohol abuse. Individuals assigned to waitlist will be put on a waitlist for 3 months after baseline assessment, after which they will also receive the same treatment as the therapy group. While they are on waitlist, they are allowed to receive other treatment/therapy. There are no restrictions for participants on the waitlist. At their baseline appointment (and subsequently at their first therapy session) they will receive a list of community referrals containing sexual health and mental health resources. Participants on waitlist will not be re-assessed for eligibility once the 3 months have passed. At therapy, participants will be given questions to answer to track their progress (OASIS, ODSIS, and Heavy Drinking- these measures can be found in the therapy manual and measurements packet). At baseline, 3 months, and 6 months, participants will complete self-report surveys at home prior to coming in to their appointment. When participants are in the office, they will be given self-report assessments of mental and behavioral health outcomes and minority stress mechanisms, computerized behavioral tasks (Implicit Associations Task, Emotional Go No-Go Task, and Self-Referent Encoding Task), and a Time-Line Follow Back (TLFB) interview of past-90-day heavy alcohol use (all of which will be administered by trained research assistants). The TLFB will be recorded for quality assurance purposes and will only show the interviewers face and capture the participants voice. Incentives will be offered for each study visit: \$25 at baseline, \$25 at 3-month follow-up, \$75 at 6-month follow-up, and \$10 for each therapy session (therapy manual has been uploaded with this application). This study will entail the recruitment of 60 SMW participants through online recruitment methods, passive poster recruitment, and an existing list of SWMs who have expressed interest and consented to be contacted for any future research studies we conduct. All aspects of Phase 3 will take place at the Yale-sponsored ESTEEM lab in New York City under the supervision of [name]. Therapy sessions will be recorded and conducted by members of the ESTEEM lab's clinical team. Therapy sessions that are videotaped will only contain the therapists face, not the participants, but will catch the participants voice. These video recordings are for supervision and quality assurance purposes. Recordings of both therapy and the TLFB are not optional. Additionally, 15-20 participants enrolled in the study will be invited at random via e-mail to complete a follow-up qualitative phone interview about their experience in the study. These interviews will be audio recorded. Participants will be receive a \$40 Amazon gift card for completing a follow-up interview.

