- Phase 3: Research data will be collected via telephone, on electronic tablets, electronic databases, survey websites, paper-and-pencil, electronic documents, and video recording. Screening data will be collected in the field using online tablets as well as collected on a secure survey website (Qualtrics.com). During the first appointment scheduling phone call, we will verify contact information in one of our password protected electronic databases at our research office. Participants will complete surveys at our study sites/offices via yale.qualtrics.com. Participants themselves will enter most data into Qualtrics.com directly. However, study staff will enter interviewer-based data (timeline follow-back of past 90 day alcohol abuse) into Qualtrics.com and one of our electronic databases during the interview. Timeline follow-back sessions will be videotaped for quality control (showing only the interviewer's face) and will be downloaded to Yale's HIPAA-compliant Secure Box drive upon retrieval from study cameras. Participant session notes will be stored in a binder unique to each participant; these binders will be stored in a locked filing cabinet. Participant and therapist post-session surveys will be entered directly into Qualtrics.com on electronic tablets. Participant tracking and scheduling data will be

recorded on a study database. One password-protected linking database containing participant names and ID codes will be kept on Secure Box and accessible only by study staff.

All study computers will be encrypted and password protected. All filing cabinets will be locked. Online surveys (yale.qualtrics.com) will use an encrypted web service (https) and will not ask participants' name or other identifying information, only participant ID number. The linking database will be kept separate from study data and will be password protected.

- 4. If identifiers will be associated with the data and/or specimens, describe whether a record or list containing a code (i.e., code number, pseudonyms) will be used, where the list will be stored, who will have access to the list and when it will be destroyed.

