In a first set of analyses, we used linear mixed models with maximum likelihood estimation and a compound symmetry covariance structure (selected based on fit criteria, i.e., lowest Akaike information criterion [AIC]) to test the Condition x Time interaction for all intervention outcomes including mental and behavioral health (e.g., depression), minority stress processes (e.g., rejection sensitivity), and universal risk processes (e.g., emotion regulation). To do so, we limited the data to baseline (time = 0) and 3 months postbaseline assessment (time = 1) and examined the Condition x Time interaction effect of receiving immediate EQuIP (condition = 1) versus receiving the 3-month waitlist (condition = 0). Thus, the estimate of interest compared preintervention to immediate postwaitlist outcomes in the immediate intervention group to prewaitlist and immediate postwaitlist outcomes in the waitlist control group. Effect sizes (d) for linear mixed models were calculated as mean pre–post change in the immediate intervention group to the mean pre–post change in the waitlist control group, divided by the pooled baseline standard deviation (Morris, 2008).

In a second set of analyses, we examined the clinical significance of observed changes in those mental health outcome measures that possess established clinical cutoffs (i.e., CES-D, ODSIS, OASIS). To do so, we used generalized linear mixed models with a logit link and binomial distribution to examine the Condition x Time interaction effect predicting the odds of meeting or

exceeding the clinical cutoff among participants receiving immediate EQuIP (condition = 1) versus those receiving the 3-month waitlist (condition = 0). For interpretability, we report proportions of participants meeting or exceeding clinical cutoff by condition and time.

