In a third set of analyses, we conducted a pooled analysis whereby data from all participants were pooled to examine change in outcome from immediate preintervention to postintervention using paired t tests (i.e., baseline to 3 months postbaseline for the immediate intervention group and 3-months postbaseline to 6-months postbaseline for the waitlist control group). Pooled analyses are useful in waitlist-controlled studies (where all participants ultimately receive treatment) to assess the pre–post effect of the intervention in a larger sample than the condition x time analyses allow. One participant assigned to the waitlist control group did not complete 3-month or 6-month assessments and was dropped from the pooled analysis (n = 59). Effect sizes (d) for pooled analyses were calculated as $\frac{2t}{\sqrt{df}}$.

Finally, we assessed the longer-term persistence of observed intervention effects by limiting analyses to immediate 3-months postbaseline (time = 1) and 6-months postbaseline (time = 2) among participants in the immediate intervention condition (condition = 1), the only participants to have completed assessments 3-months after receiving the intervention. Specifically, we examined the significance of changes between time points for all outcomes, including mental and behavioral health (e.g., depression), minority stress processes (e.g., rejection sensitivity), and universal processes (e.g., emotion regulation). Results were evaluated at p < .05.

References

Braun, V., & Clarke, V. (2006). Using thematic analysis in psychology. *Qualitative Research in Psychology*, *3*(2), 77-101.

Field, A. (2013). Discovering statistics using IBM SPSS statistics. SAGE.

George, D., & Mallery, P. (2010). SPSS for Windows step by step. A simple study guide and reference (10. Baskı). *GEN, Boston, MA: Pearson Education, Inc.*

Morris, S. B. (2008). Estimating effect sizes from pretest-posttest-control group designs. *Organizational Research Methods*, *11*(2), 364-386. https://doi.org/10.1177/1094428106291059

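### For alcohol, the 3-versus-6-month persistence comparison sets mostly during-therapy drinking against post-therapy drinking, because the TLFB looks back 90 days

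*Protocol*

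**What the plan says.** **Protocol, Section IV.3 (Research Plan), Phase 3.** The immediate arm receives "10 weekly individually-delivered sessions, directly after baseline assessment". The waitlist arm starts the same therapy after 3 months. Visits fall at baseline, 3 months and 6 months: "At baseline, 3 months, and 6 months, participants will complete self-report surveys at home". The in-office part includes the "Time-Line Follow Back (TLFB) interview of past-90-day heavy alcohol use".

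**Protocol, Section VI.3 (how data are collected and recorded), Phase 3.** The window is given again as "timeline follow-back of past 90 day alcohol abuse". No shorter window is set for any particular visit.

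**Protocol, Section IV.3, at therapy sessions.** Participants also receive "questions to answer to track their progress (OASIS, ODSIS, and Heavy Drinking" items. These exist only while someone is in therapy, and the SAP does not list the drinking item.

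**SAP, Intervention Efficacy.** Three analyses use the visit that ends therapy:
- The main contrast: "we limited the data to baseline (time = 0) and 3 months postbaseline assessment (time = 1"), testing Condition x Time for every outcome, behavioural health included.
- The pooled analysis: "to examine change in outcome from immediate preintervention to postintervention using paired t tests", over 0 to 3 months in the immediate arm and 3 to 6 months in the waitlist arm.
- The persistence analysis: change from 3 to 6 months in the immediate arm only, again for every outcome. The 6-month visit is treated as 3 months after therapy.

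The SAP does not name its alcohol variable, and neither document mentions the overlap between the look-back and the therapy period.

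**The concern.** A 90-day recall taken about 90 days after baseline describes the period in which therapy was delivered, plus a short tail. It does not describe a participant's state once therapy is over. At the visit that ends therapy (3 months in the immediate arm, 6 months in the waitlist arm), the value labelled as post-intervention is therefore mostly a during-therapy value.

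This matters most for persistence. That analysis asks whether gains present at the end of therapy are still there later. For alcohol, its starting point averages over the weeks in which the effect may still have been building. A later return of drinking can then be offset by the weaker starting value. No control arm can correct for this, because the waitlist arm is in therapy from month 3. Alcohol is one of the problems the therapy targets, and heavy drinking is an entry criterion. A reader could take an unchanged 3-to-6-month result as evidence of durability while drinking was in fact returning.

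**Working it through.** The plan gives no effect size, onset or variance for alcohol. Its only power figure concerns depression, so there is no plan figure to reproduce here. The overlap follows from the schedule, but its consequences depend on an assumed onset.

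**Step 1: overlap.** Ten weekly sessions span 9 x 7 = 63 days from first to last, or 70 days as ten full weeks. Taking 3 months as day 90, 63/90 = 70% and 70/90 = 78% of the look-back lies within therapy. That leaves 27 or 20 days (30% or 22%) after it. The windows at successive visits barely overlap, so the baseline value is clean.

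**Step 2: share of the end-of-therapy effect captured at 3 months.** Set the full effect to 1 and assume it grows as min(t/T, 1), then holds. The mean over days 0-90 is 1 - T/180. For T between 60 and 90, the mean over days 60-90 is 1 - (T - 60)²/(60T).

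| Assumed onset | 90-day window | Understatement | Last 30 days |
|---|---|---|---|
| Immediate | 100% | 0% | 100% |
| Linear to day 35 | 1 - 35/180 = 80.6% | 19% | 100% |
| Linear to day 63 | 1 - 63/180 = 65.0% | 35% | 1 - 9/3780 = 99.8% |
| Linear to day 70 | 1 - 70/180 = 61.1% | 39% | 1 - 100/4200 = 97.6% |

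If the effect appeared only once therapy ended, the 90-day window would capture 22-30% and the last 30 days 67-90%. I treat that as an extreme and do not rely on it.

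**Step 3: persistence.** Let s be the share captured at 3 months. The 6-month window covers days 90-180.
- Fully maintained effect: the 6-month mean is 1, so the apparent further gain is 1 - s, which is 0%, 19%, 35% or 39% for the four rows.
- No apparent change: the mean over days 90-180 must equal s, an average loss of 1 - s. If the effect falls in a straight line from 1 at day 90 to r at day 180, then (1 + r)/2 = s and the loss by day 180 is 1 - r = 2(1 - s) = T/90. That is 39% (T = 35), 70% (T = 63) or 78% (T = 70).
- The same losses seen through 30-day windows: the mean over days 150-180 is 1 - (75/90)(1 - r). For T = 63 this is 0.417 against 0.998 at 3 months, and for T = 70 it is 0.352 against 0.976. The short window would show a loss of 58-62% of the full effect where the 90-day window shows none.

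**Step 4: cost in precision.** For a window of W days, take SD² = b² + [p(1 - p) - b²]/W, where p is the proportion of heavy-drinking days and b the between-person SD. The standardised 30-day effect relative to the 90-day one is (s30/s90) x (SD90/SD30). With p = 0.10-0.20 and b = 0.05-0.15 (assumptions), SD90/SD30 runs from √(0.00425/0.00775) = 0.74 to √(0.02325/0.02475) = 0.97.
- Immediate onset: 0.74-0.97.
- Linear to day 35 (x 1/0.806): 0.92-1.20.
- Linear to day 70 (x 0.976/0.611): 1.18-1.55.

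Entry requires only one heavy-drinking episode in 90 days (1/90 = 1.1%), so p may be much lower. At p = 0.02, with b from half the mean to the mean, the three ranges become 0.65-0.77, 0.81-0.95 and 1.04-1.23. The chance of no heavy-drinking day is 0.98^30 = 55% in 30 days, against 0.98^90 = 16% in 90 days.

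**The case against.** The strongest reply has four parts.

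**The analysed variable is not confirmed.** The SAP does not name it, and the protocol refers to further self-report behavioural measures and a measurements packet. This stands. The 90-day TLFB count is the only alcohol measure named for the visits, but its use as the outcome is inferred.

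**The randomised contrast is sound.** A reader might infer that the 3-month alcohol comparison is biased or invalid. The documents do not support that. Both arms and all visits use the same window, it matches the 90-day entry criterion, and baseline is not contaminated. The contrast estimates an average effect over the treatment period. It can fall short of the end-of-therapy effect only if onset is gradual, and under that model the error is towards a smaller effect, not a false positive.

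**A 30-day score is not simply better.** A reader might infer that it should replace the 90-day count throughout. Step 4 shows otherwise: it loses precision if onset is immediate, may lose it with build-up to day 35, and produces more zeros. The SAP is also written in the past tense and already reports baseline differences, transformed outcomes and a dropped participant. Swapping the outcome of the main contrast now would be a post hoc change. The documents also do not say that day-level TLFB entries were kept.

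**The analysis is secondary.** Phase 3 was sized mainly for feasibility and acceptability, and persistence is an uncontrolled comparison in one arm of 30. This limits the importance, but it does not answer the mismatch. Extra noise in a shorter window is no reason to use a window that covers the wrong period.

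**Conclusion.** The concern holds for persistence and, in a weaker form, for the other two analyses. On the documents' own schedule, 70-78% of the look-back at the visit that ends therapy lies within therapy. For alcohol, the 3-to-6-month comparison therefore does not compare end of therapy with follow-up. A maintained effect could look like a further gain of 0-39% of the full effect. An average loss of that size over days 90-180 could look like no change, which under linear onset to day 63-70 means a straight-line loss of about 70-78% by day 180.

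The main 3-month contrast needs only a correct label. As an estimate of the end-of-therapy effect it may be low by 0% (immediate onset), 19% (build-up to day 35) or 35-39% (linear to day 63-70). It would go too far to say that dilution is established, since it vanishes if the full effect is present from the start. The pooled analysis needs the same label, because in both arms its post value covers that arm's own therapy.

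The conclusion assumes that the 90-day TLFB count is the analysed alcohol outcome and that sessions run roughly weekly. The sizes rest on the assumed onset curves.

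**What to change.** 1. Name the alcohol variable and its window in the SAP.
2. Keep the 90-day count as the outcome in the randomised 3-month contrast, and describe it there and in the pooled analysis as a treatment-period average.
3. If day-level TLFB entries were kept, base the alcohol persistence comparison on heavy-drinking days in the last 30 days before each visit. Report the same 30-day score as a sensitivity analysis for the 3-month and pooled contrasts, marked as added later.
4. If day-level entries were not kept, make no persistence claim for alcohol from the 90-day values.

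The cost is some SAP wording and, under item 3, one derived variable with no new data collection. The downside is a noisier score with more zeros. At the visit that ends therapy it still includes about 3 to 10 therapy days, more if sessions slip. This is a cheap improvement that changes what can be concluded about durability for alcohol and leaves the main contrast as it is.

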☑ Through local NGO or other local contact	☐ Departmental/Center research boards	□ Newspape
☑ Table set-up / in-person recruitment of	☐ Snowball sampling	
public		
☐ Classroom recruitment	☑ Social Media (Twitter/Facebook):	

3. Targeted Enrollment: Give the number of participants:

a. Targeted for enrollment at Yale for this protocol

Phase 1: 20 sexual minority women **Phase 2:** 10 SMW experts **Phase 3:** 60 sexual minority women b. If this is a multi-site study, give the total number of participants targeted across all sites N/A

4. How was this estimate derived?

 \square Other:

For both Phase 1 and Phase 2, estimates were derived based on the number of interviews required to reach saturation in previous intervention development studies. For Phase 3, this part of the study is powered primarily to examine feasibility and acceptability. This phase will also allow us to determine the preliminary efficacy of the intervention. We will use Cohen's d and Hedge's g corrected for sample size, both of which express the average amount of individual change between intervention and control groups in terms of units of standard deviation. Group means on continuous variables typically begin to stabilize by 20-30 participants, and our waitlist design enables us to estimate effect sizes both by comparing intervention and control conditions at 3-months (n = 30/condition) and by examining pre-post effect sizes for the entire sample (n = 60). Our sample size provides sufficient power (1 - β =.8) to detect

intervention effects consistent with effect size estimates identified in our intervention research with sexual minority men in which the relative reduction in depression was 0.55 between intervention and control groups.

5. Process of Consent/Assent (NOTE: When a study includes minors, parent provide permission [not consent] for the child's participation, and the child provides assent for participation)

Describe the setting and conditions under which consent/assent will be obtained, including parental permission or surrogate permission and the steps taken to ensure participants' independent decision-making.

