NCT03721276

Title of Research Project: Project EQuIP: Empowering Queer Identities in Psychotherapy

SAP Date 10.7.2019

Statistical Analysis Plan

Feasibility and Acceptability

Feasibility was assessed in terms of treatment attendance. Acceptability was assessed in terms of responses to the quantitative exit survey that all participants completed at 6-month follow-up and the qualitative exit interview conducted with 20 randomly selected participants after 6-month follow-up. Qualitative exit interviews were transcribed verbatim, and the third and eighth authors served as coders and double-coded all transcripts. Thematic analysis was used to identify patterns of responses, and emergent codes were categorized into larger themes (Braun & Clarke, 2006).

Intervention Efficacy

We assessed intervention efficacy using an intent-to-treat analysis including all eligible cases (n = 60). First, to determine randomization effectiveness, differences in baseline demographic characteristics were assessed between the immediate intervention (n = 30) and waitlist control (n = 30) conditions using t tests for continuous measures and chi-square tests for categorical measures. Income and gender identity differed between conditions (p < .05), with the waitlist control group reporting higher income and having a larger proportion of cisgender women; thus, we included income and gender identity as covariates in subsequent analyses.

Dependent variables were assessed for normality using skewness and kurtosis thresholds of ± 2 (Field, 2013; George & Mallery, 2010). Suicidality and internalized stigma were found to be non-normal; we therefore log-transformed these variables for further statistical tests (reassessment of skewness and kurtosis after transformation showed normal distribution).

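### The stated 80% power for an effect of 0.55 does not follow from 30 per condition: the 3-month comparison has about 55%, and the SAP's Condition x Time test reaches 80% only at an unstated pre-post correlation of about 0.72

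*Protocol*

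**What the plan says.** Section V, item 4 of the protocol (how the enrolment estimate was derived) states that for Phase 3 "this part of the study is powered primarily to examine feasibility and acceptability", and that efficacy is preliminary. It names Cohen's d and Hedges' g as effect measures, "both of which express the average amount of individual change between intervention and control groups in terms of units of standard deviation". It says that effect sizes can be estimated in two ways: "by comparing intervention and control conditions at 3-months (n = 30/condition"), and "by examining pre-post effect sizes for the entire sample (n = 60"). It then makes the power claim, "Our sample size provides sufficient power (1 - β =.8) to detect" effects consistent with the team's research in sexual minority men, in which "the relative reduction in depression was 0.55 between intervention and control groups".

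The SAP, under Intervention Efficacy, compares baseline characteristics "between the immediate intervention (n = 30) and waitlist control (n = 30) conditions", which confirms the arm sizes. Its between-arm analysis uses linear mixed models on the baseline and 3-month data "to test the Condition x Time interaction for all intervention outcomes". It divides the difference in mean change by the pooled baseline SD to obtain d, and evaluates results at p < .05. Neither document states sidedness or a pre-post correlation.

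**The concern.** The power sentence cannot be checked without supplying inputs that it omits. With the most natural choices, the comparison that the paragraph names falls well short of 80%. The sentence also follows directly after two different comparisons, one controlled and one not, and does not say which of them has 80% power.

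At stake is how a non-significant between-arm result would be read. Someone who accepts 80% puts the chance of missing a true effect of 0.55 at 20%. For the unadjusted 3-month comparison it is about 45% (1 - 0.554). A null result could then be taken as evidence against an effect of 0.55 when the design had little better than an even chance of detecting it.

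**Working it through.** **Inputs.** From the protocol, Section V, item 4: 30 per condition, 60 in total, effect 0.55, power 0.80. From the SAP, Intervention Efficacy: level 0.05, Condition x Time test, d in pooled baseline SD units. Assumed here: 0.55 is a standardized mean difference; tests are two-sided, with one-sided also shown; SDs are equal at baseline and 3 months; the pre-post correlation r is shown as a range.

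**1. Between-arm comparison at 3 months.** Two-sample t test, df = 2 × 30 - 2 = 58, noncentrality = d × √(n/2).

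- Noncentrality = 0.55 × √15 = 2.130.
- Two-sided 5%: critical value 2.002, power 0.554 (normal approximation 0.568).
- One-sided 5%: critical value 1.672, power 0.677.
- The plan's 0.80 is not reproduced. A two-sided alpha of about 0.20 would be needed to reach it.
- Effect detectable with 80% power: d = 0.736 two-sided, 0.650 one-sided.
- Smallest n per condition for 80% at d = 0.55: 53 two-sided (power 0.801; 52 gives 0.793), 42 one-sided (0.804).

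**2. The SAP's Condition x Time test.** With two time points this is in essence a comparison of mean change. If 0.55 is in baseline SD units, the SD of change is √(2(1 - r)) baseline SDs, so the effect in SD-of-change units is 0.55 / √(2(1 - r)). Two-sided 5%, 30 per condition:

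| Assumed r | Effect in SD-of-change units | Power |
|---|---|---|
| 0.3 | 0.465 | 0.425 |
| 0.5 | 0.550 | 0.554 |
| 0.6 | 0.615 | 0.649 |
| 0.7 | 0.710 | 0.772 |
| 0.72 | 0.735 | 0.799 |
| 0.75 | 0.778 | 0.842 |
| 0.8 | 0.870 | 0.912 |

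Power of 80% requires 0.55 / √(2(1 - r)) = 0.736, hence r = 1 - (0.55/0.736)²/2 = 0.72. One-sided, the threshold is 0.64. Simulation with 200,000 replicates per row agrees with the table to within 0.002.

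**3. If 0.55 is already in SD-of-change units**, which the protocol's description of d would allow, r drops out and power is 0.554 whatever its value.

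**4. Pre-post analysis of all 60.** Paired t test, noncentrality = effect × √60.

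- Standardized change of 0.55: noncentrality 4.260, power 0.987 (0.986 with the 59 in the SAP's pooled analysis).
- 0.55 in baseline SD units with r = 0: effect 0.55/√2 = 0.389, power 0.842. Power rises with r: 0.943 at 0.3 and 0.987 at 0.5.
- Change detectable with 80% power: 0.368.

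This analysis exceeds 80%, but it has no control group.

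**The case against.** The strongest reply is that this is an under-specified statement and not a wrong one. The protocol never labels 0.55 as d, and the figure comes from research that the documents do not reproduce. A test that uses the baseline can legitimately have more power than a 3-month comparison alone; at r of about 0.72 the SAP's test delivers 80%. The pre-post analysis exceeds 80% outright. It is therefore true that 80% is not impossible, and the conclusion has to be conditional.

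The correlation threshold is also not exact. With maximum likelihood variance and a normal reference it is 0.705. With a 3-month SD of 0.8 to 1.2 times the baseline SD it runs from about 0.68 to 0.78. A baseline-adjusted comparison, which the SAP does not specify, would need 0.66. All of these are substantial correlations that neither document states or justifies, so they shift the threshold without supporting the claim.

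On scale, the paragraph names d and g and presents 0.55 as an effect size estimate, so d is the natural reading. If another scale was meant, the sentence cannot be checked at all and still needs rewriting. The pre-post route does not fit, because 0.55 is described as a difference between intervention and control.

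Finally, Phase 3 is aimed mainly at feasibility and acceptability, the SAP repeats no power claim, and the misreading of a null result is only a possibility. That lowers the stakes. It does not make the stated 80% correct for the between-arm comparison.

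**Conclusion.** The concern holds. No between-arm test at the 5% level, one-sided or two-sided, reaches 80% power for 0.55 from the inputs that the documents give. The comparison that the protocol names falls short by about 25 points two-sided and 12 points one-sided. The SAP's own test gets there only with a pre-post correlation of about 0.72 (0.64 one-sided), and not at all if 0.55 is in SD-of-change units.

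This rests on two inferences, that 0.55 is a standardized mean difference and that the SAP's 5% level applies to the protocol's sentence, and for the 0.72 also on equal SDs over time. The point should be fixed. Its consequence is modest, because efficacy is preliminary and neither the sample size nor the analysis depends on the correction.

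**What to change.** Restate the power sentence along these lines: *With 30 per condition and two-sided alpha .05, the unadjusted 3-month comparison has about 55% power for d = 0.55 and 80% power for d of about 0.74.*

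If the Condition x Time test is the intended basis, give its power instead, with the assumed correlation and its justification, the sidedness, and whether d is in baseline SD or SD-of-change units. If the sentence refers to the pre-post analysis of all 60, say so and say that it is uncontrolled. Unless a justified correlation gives at least 80%, add that a non-significant between-arm result should not be read as evidence against an effect of 0.55.

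The cost is the rewording of one paragraph and, probably, a less favourable stated power for the between-arm comparison. No participants are added and the analysis does not change.
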